8.2. Data Collection

All data will be collected using the UCD Database System (eVELOS) forms.

9. Statistical Considerations

9.1. Study endpoints

Primary endpoints

(1) Grade ≥ 3 radiation pneumonitis, (2) grade ≥ 3 esophagitis, (3) other grade ≥ 3 AEs that occur ≤ 12 months after treatment and drop-out defined as definitely, probably, or possibly related to the protocol treatment.

Secondary endpoints

- 1) Long-term toxicity, as scored by the NCI-CTCAE version 4.0.
- 2) Clinical and subclinical endpoints for pulmonary toxicity (including radiation pneumonitis and post-treatment changes in PFTs, 6-min walk test, and BODE index).
- 3) Correlation between the clinical/subclinical endpoints for pulmonary toxicity and functional dose-volume parameters.

- 4) Local tumor control.
- 5) Lung functional dose-volume metrics, including the functional V_x (fV_x) (% volume receiving $\geq x$ Gy) and functional mean lung dose (fMLD).

9.2. Patient accrual

We aim to accrue 34 patients over 1.5 years. Patient accrual will continue until either the projected sample of 34 patients has been enrolled, or the number of patients developing Grade ≥ 3 AEs or drop-out due to intolerance of treatment exceeds five. Patient follow-up will continue until all patients have at least two years of follow-up, to allow for assessment of longer-term AEs.

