7.2. Adverse Event Definitions

Adverse Events (AEs)

Any unfavorable and unintended sign (including an abnormal laboratory finding), symptom, or disease temporally associated with the use of a medical treatment or procedure regardless of whether it is considered related to the medical treatment or procedure (attribution of unrelated, unlikely, possible, probable, or definite).

Serious Adverse Events (SAEs)

Any adverse experience occurring during any part of the protocol treatment and 30 days after that results in any of the following outcomes:

- Results in death.
- Is life-threatening (refers to an AE in which the patient was at risk of death at the time of the event. It does not refer to an event which hypothetically might have caused death if it were more severe).
- Requires inpatient hospitalization or prolongation of an existing hospitalization
- Results in persistent or significant disability or incapacity. (Disability is defined as a substantial disruption of a person's ability to conduct normal life functions).
- Is a congenital anomaly/birth defect.
- Is a medically important event. This refers to an AE that may not result in death, be immediately life threatening, or require hospitalization, but may be considered serious when, based on appropriate medical judgment, may jeopardize the patient, require medical or surgical intervention to prevent one of the outcomes listed above, or involves suspected transmission via a medicinal product of an infectious agent.

Intensity (Severity) of the Adverse Event

The intensity or severity of AEs will be graded according to the NCI-CTCAE version 4.0 criteria.

Adverse Event Documentation

All AEs occurring after the subject has received the first dose of investigational treatment will be fully recorded in the subject's case record form. Documentation will be supported by an entry in the subject's file. Each event will be described in detail along with start and stop dates, severity, relationship to study treatment, action taken and outcome.

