9.4. Sample size

We will examine the safety of 4D CT ventilation image-guided personalized radiotherapy based on AEs during the first 12 months of follow-up and toxicity-related drop-out. With a sample size of 34 patients, we will be able to see grade ≥ 3 radiation pneumonitis, grade ≥ 3 esophagitis and other grade ≥ 3 AEs at least once with 94%, 99% and 99% probabilities, respectively, assuming

true rates of 13%, 21% and 20%, respectively. We can also estimate these AE rates with a standard error of 8%, 9% and 9%, respectively.

Approximately 37% of patients are estimated to die over the first 12 months of follow-up according to the published survival data for patients with locally advanced NSCLC (Machtay *et al.*, 2012). Also 1% of patients are estimated to drop out for reasons unrelated to the protocol treatment. To compensate for possible loss of patients for such reasons, a sample size of 34 (increased by 38% from 20) will be used.

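### Section 9.4 states sample size and precision as if the accrual limit in 9.2 did not exist, and 9.2 counts a looser set of events than the primary endpoints

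*Combined protocol and SAP*

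**What the plan says.** Section 9.2 aims for 34 patients over 1.5 years. Accrual ends at 34, or earlier if the number of patients with Grade 3 or higher "AEs or drop-out due to intolerance of treatment exceeds five". This is one pooled count, reached at the sixth affected patient, with no attribution and no time window.

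Section 9.4 assumes "true rates of 13%, 21% and 20%, respectively" for pneumonitis, esophagitis and other events. It gives 94/99/99% probabilities of seeing each at least once in 34 patients and adds: "We can also estimate these AE rates with a standard error of 8%, 9% and 9" (per cent). Its allowance for loss is 37% deaths in the first 12 months and 1% unrelated drop-out: "a sample size of 34 (increased by 38% from 20) will be used". It does not mention the 9.2 limit. Section 9.5 describes interim reports and gives no operating characteristics.

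Sections 9.1 and 9.3 define three separate primary endpoints, carrying a 12-month window and "drop-out defined as definitely, probably, or possibly related to the protocol treatment". Section 9.4 refers to "AEs during the first 12 months of follow-up and toxicity-related drop-out". Section 7.2 defines an AE "regardless of whether it is considered related to the medical treatment or procedure".

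**The concern.** There are two linked problems.

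First, the rates used in 9.4 to describe what the trial will deliver are rates at which 9.2 would often end enrolment. If the event types fall mostly in different patients, the trial would usually close well short of 34, and the stated sample size and standard errors would not be what the design yields.

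Second, the events counted in 9.2 are not the events analysed in 9.3. Two people applying 9.2 in good faith, one counting all Grade 3 or higher AEs and the other only related ones within 12 months, could close accrual at different times. On the literal reading, unrelated events could close it while related toxicity is well below the 9.3 ceilings.

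**Working it through.** **Inputs.** From 9.4: rates 13%, 21% and 20%, N = 34, base of 20, 37% deaths and 1% unrelated drop-out (38% loss). From 9.2: close at the sixth affected patient; 34 patients in 18 months. From 7.3: severe esophagitis peaks 4–8 weeks from the start of treatment; about 80% of pneumonitis appears within 10 months. The documents give neither the overlap between event types nor the CFRT/SABR split.

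**The plan's own figures.** SE = √(p(1−p)/n); P(at least one) = 1−(1−p)^n.

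- n = 20: SE 7.5/9.1/8.9%; P = 93.8/99.1/98.8%. These match 8/9/9% and 94/99/99% to rounding.
- n = 34: SE 5.8/7.0/6.9%; P = 99.1/99.97/99.95%. These do not match.

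So the stated figures describe 20 evaluable patients. Reading 38% as the loss fraction, 20/0.62 = 32.3, close to 34.

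**Chance that a patient has any counted event, q.** Complete overlap gives the largest rate, 21%. Independence gives 1 − 0.87 × 0.79 × 0.80 = 45.0%. Expected affected patients among 34: 34 × 0.21 = 7.1, or 34 × 0.45 = 15.3, where a sixth closes accrual.

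**Reaching the limit.** The no-lag column is the binomial P(X ≥ 6 | 34, q). The timed column is the probability that the sixth affected patient appears before patient 34 enters, from 40,000 simulated trials per scenario. Ranges in a cell run from 37% 12-month mortality to no deaths.

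| True rates | q, overlap / independence | No lag, overlap / independence | Timed, overlap / independence |
|---|---|---|---|
| 13/21/20% | 21.0% / 45.0% | 75% / >99.9% | 61–66% / 97–99% |
| One half | 10.5% / 24.7% | 14% / 88% | 8–10% / 48–61% |
| One third | 7.0% / 17.0% | 3% / 53% | 2% / 16–24% |

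The timing takes esophagitis at 4–8 weeks and 80% of pneumonitis by 10 months from 7.3. The rest is assumed: even accrual, a 6-week course for everyone, pneumonitis no earlier than 1 month after treatment with the remaining 20% in months 10–12, other AEs uniform over 12 months, and exponential deaths. Median enrolment at full rates is 29–31 (overlap) or 20–21 (independence).

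**A check by hand.** Suppose every event becomes known after a fixed lag. Six months is 6 × 34/18 ≈ 11 patients, so the limit must be reached among the first 33 − 11 = 22: P(X ≥ 6) is 31% at q = 21% and 97% at q = 45%. Nine months is 17 patients, leaving 16: 10% and 80%.

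**Later timing.** Placing one event time per patient evenly over 12 months after a 6-week course gives 9% to 21% under overlap and 73% to 92% under independence, at full rates.

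**Precision after 38% loss.** 20 enrolled × 0.62 = 12.4 evaluable: SE 9.6/11.6/11.4%. 29 enrolled × 0.62 = 18.0: SE 7.9/9.6/9.4%, against 8/9/9% planned.

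**Unrelated AEs.** Suppose a further 10% of patients have an unrelated Grade 3 or higher AE (assumed, uniform over 12 months). At one third of the rates, closure before patient 34 rises from about 2%–24% to about 18%–61% with the timing above.

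**The case against.** The strongest reply is that 13/21/20% are the ceilings in 9.3, taken from locally advanced disease, while SABR patients with early-stage or limited metastatic disease are also eligible. A trial that often closes at its ceiling rates is behaving as a safety trial should. Section 9.2 openly makes 34 a maximum, follow-up and estimation continue after closure, and the Data Safety Monitoring Committee has oversight. A broad trigger may be deliberate. All of this stands, and nothing here shows that the limit is wrongly set. It does not answer the point that 9.4 uses those same rates to state a sample size and precision with no reference to the limit, or that 9.2 does not say its broader count is intended.

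The timed figures may also lean high. They count events at onset, whereas post-treatment AEs are assessed every three months (11.4). If post-treatment events registered only at the next visit, stopping at full rates under overlap would fall from 61–66% to about 55–60%. That is an extreme case, because 7.3 promises prompt evaluation of symptoms. The direction is unchanged.

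Two stronger readings are tempting but unsupported. A reader might infer that accrual cannot close under 9.2 while 9.3 is met on the exact upper confidence limit. That holds only if both sections count the same events. Six unrelated AEs and no related ones in 34 patients would close accrual, yet the upper limit for 0 of 34 is 1 − 0.025^(1/34) = 10.3%, below all three ceilings. A reader might also take the no-lag count with 10% unrelated AEs at one third of the rates, 49% to 89%, as the chance of early closure. It includes events arising after the last patient has entered; the timed range is 18% to 61%.

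**Conclusion.** The point holds. Section 9.4 describes a design without the 9.2 limit, at rates where that limit usually binds unless event types coincide in the same patients and occur late. The omission and the mismatch in event definitions rest on the text alone. The size rests on assumed overlap and timing: early closure in about 61% to 99% of trials at the 9.4 rates under 7.3-guided timing, down to about 9% under complete overlap with later events, and about 2% to 24% at one third of the rates.

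It should not be read as a general loss of precision: at about 29 enrolled, precision is nearly as planned. Nor is the arithmetic in 9.4 wrong for 20 evaluable patients; the figures are attached to 34.

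The mismatch stands even though 9.1 and 9.3 leave unclear whether the window and attribution cover all three endpoints or only the third, since 9.2 carries neither. Section 9.3 also leaves open its denominator and whether the estimate or the confidence limit decides. That is a separate gap, and this point does not depend on it. The matter should be fixed.

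**What to change.** 1. Clarify in 9.1 and 9.3 whether the 12-month window and relatedness apply to all three endpoints. Then have 9.2 count those same events, or state that a broader safety count is intended.
2. For the existing limit, tabulate the stopping probability and expected enrolment at 13/21/20% and at lower and higher rates, under stated overlap and timing. Restate the expected sample size and precision in 9.4 accordingly, noting that 8/9/9% and 94/99/99% correspond to 20 evaluable patients.
3. State how closure under 9.2 bears on the 9.3 conclusion.

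The choice of limit stays with the investigators and the Data Safety Monitoring Committee. The cost is amendment text and one table, with no extra patients or procedures. The stated sample size and precision will look less favourable, and a narrower count could let more patients with AEs judged unrelated accrue before closure.

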9.3. Analysis plan

Primary endpoints: (1) Grade ≥ 3 radiation pneumonitis, (2) grade ≥ 3 esophagitis, (3) other grade ≥ 3 AEs that occur ≤ 12 months after treatment and drop-out defined as definitely, probably, or possibly related to the protocol treatment.

We will estimate the rates of AEs and tolerability with exact 95% confidence intervals. 4D CT ventilation image-guided personalized radiotherapy will be considered safe if AE rates are lower than the following acceptable rates (determined based on the published toxicity data for locally advanced lung cancer patients): (1) grade ≥ 3 radiation pneumonitis, 13% (Jiang *et al.*, 2012), (2) grade ≥ 3 esophagitis, 21% (Wei *et al.*, 2006), and (3) other grade ≥ 3 AEs and drop-out, 20% (Bradley *et al.*, 2015).

Secondary endpoints

Analyses of secondary endpoints will be primarily descriptive rather than hypothesis testing.

Toxicity will be summarized by frequency and exact 95% confidence intervals, overall and separately by grade and organ system.

The clinical significance of 4D CT ventilation image-guided personalized radiotherapy will be estimated by evaluating: (1) clinical and subclinical endpoints for pulmonary toxicity (including radiation pneumonitis, PFTs, 6-min walk test, and BODE index); (2) correlation between those endpoints and functional dose-volume parameters. Radiation pneumonitis will be assessed at follow-up every 3 months for a minimum of 2 years after treatment using the NCI-CTCAE version 4.0. Post-treatment changes in PFTs (including spirometry, lung volumes and diffusing capacity), 6-min walk test, and the BODE index will be evaluated at the time of 6-month follow-up. Using composite treatment plans, the following lung functional dose-volume parameters will be calculated: functional mean lung dose (fMLD), functional V_{20} (fV_{20}) and functional effective dose (fD_{eff}) (Vinogradskiy *et al.*, 2013), which will be correlated with the endpoints for pulmonary toxicity.

To quantify the dosimetric significance of 4D CT ventilation image-guided adaptive radiotherapy, we will create: (1) 4D CT ventilation image-guided adaptive radiotherapy plan, (2) 4D CT ventilation image-guided non-adaptive radiotherapy plan, and (3) anatomical image-guided non-adaptive radiotherapy plan. We will evaluate the lung functional dose-volume parameters, including the functional V_x (fV_x) (% volume receiving $\geq x$ Gy) and functional mean lung dose (fMLD) for each plan. The lung functional dose-volume parameters of the 4D CT ventilation image-guided adaptive radiotherapy plans will be compared with those of the 4D CT ventilation image-guided non-adaptive radiotherapy plans and anatomical image-guided non-adaptive radiotherapy plans using a paired *t*-test. Furthermore, we will also investigate sensitivity to the number (1 or 2) and time (16-20 Gy and/or 30-34 Gy) of plan adaptation to design an optimal adaptive radiotherapy strategy, *e.g.*, when and how many time(s) to adapt the original plan.

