3.1. Inclusion criteria

- 1) Primary lung cancer or metastatic disease to the lungs to be treated with either conventionally-fractionated radiotherapy (CFRT) or hypo-fractionated stereotactic ablative radiotherapy (SABR).
- 2) Age restriction and/or gender/ethnic restrictions: Patients must be ≥ 18 years of age. There are no gender or ethnic restrictions.
- 3) Concurrent chemotherapy is allowed, but not required.
- 4) Life expectancy with treatment should be ≥ 6 months in the estimation of the treating physicians.
- 5) Zubrod performance status ≤ 2
- 6) Adequate marrow and hepatic function defined as Hgb ≥ 8 ; platelets $\geq 100k$; ANC ≥ 1500 ; LFTs $\leq 2x$ upper limit of normal and creatinine ≤ 2.0 or creatinine clearance of ≥ 40
- 7) Patient must be able to provide study specific informed consent prior to study entry.

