3.2. Exclusion criteria

- 1) Prior radiotherapy for thoracic cancer or other malignancy leading to any overlap of planned radiotherapy fields.
- 2) For patients undergoing definitive CFRT, patients with distant metastatic disease are not eligible.
- 3) For patients undergoing SABR, both early stage primary lung cancer patients and those with limited metastatic disease to the lungs are eligible; however, patients with oligometastatic disease should have a controlled primary and no more than one other involved organ system.
- 4) Children (< 18 years of age), pregnant women, University of California employees and students, and prisoners will be excluded from this study.
- 5) We will carefully consider the inclusion of patients with severe artifacts in 4D CT images, which deteriorate the accuracy of ventilation computation.

4. Imaging Procedures

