11.1. Pre-treatment assessments

Staging workup will include PET/CT, MRI of the brain (this is only required for locally advanced patients and for other patients, it is optional), and CT of the chest and upper abdomen performed with contrast (recommended, but not required) within 8 weeks prior to registration, as well as histologic or cytologic documentation of lung cancer. PFT to include routine spirometry, lung volumes, and diffusing capacity should be performed within 8 weeks before treatment. CBC with differential and comprehensive metabolic panel will be obtained within 14 days of enrollment to ensure adequate marrow reserve and end organ function.

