APPENDIX II:

Eligibility Checklist

- _____ (Y) 1. Does the patient have histologically documented primary lung cancer (NSCLC or SCLC)? or histologically documentation of a solid tumor with clear radiographic evidence of spread to the lungs amenable to SBRT (for SBRT patients only; if CT-guided lung biopsy is deemed unsafe by interventional radiology, documented multidisciplinary review confirming radiographic diagnosis of early stage lung cancer or lung metastasis may be used)
- _____ (Y) 2. Is definitive thoracic radiotherapy planned?
- Conventionally-fractionated radiotherapy (CFRT) (with or without concurrent chemotherapy)
 - Stereotactic ablative radiotherapy (SABR)
- _____ (Y) 3. Is the patient ≥ 18 years of age?
- _____ (Y) 4. Is the life expectancy with treatment ≥ 6 months?
- _____ (Y) 5. Is the Zubrod performance status 0-2?
- _____ (Y) 6. Does the patient have adequate marrow reserve defined as an ANC ≥ 1500 , plt $\geq 100,000$, Hgb ≥ 8 g/d?
- _____ (Y) 7. Does the patient have adequate end organ function defined as LFTs $\leq 2x$ upper limit of normal and creatinine ≤ 2.0 or creatinine clearance ≥ 40 ?
- _____ (Y) 8. Is the patient able to provide study specific informed consent?
- _____ (N) 9. Has the patient had prior radiotherapy or other malignancy leading to any overlap of planned radiotherapy fields?
- _____ (Y/N) 10. Is concurrent chemotherapy planned?
- _____ (Y/N) 11. Was a CT with contrast of lung and upper abdomen performed within 8 weeks of registration? (Recommended)
- _____ (Y) 12. Was an FDG-PET performed for staging within 8 weeks of registration?
- _____ (Y) 13. Does the patient have locally advanced disease?
- _____ (Y) 14. If yes on #13, was an MRI or CT of the brain performed for staging within 8 weeks of registration?

- _____ (N) 15. Does the patient have any evidence of malignant pleural or pericardial effusion?
- _____ (N) 16. Does the patient have radiographic evidence of distant metastases?
- _____ (Y/NA) 17. Has the patient agreed to use an effective method of contraception?
- _____ (N) 18. If female, is the patient pregnant or lactating?

**APPENDIX III:
Patient Assessments**

Assessments	Pre-study entry	At time of simulation	Mid-RT (8-10 fx)	Mid-RT (15-17 fx)	Weekly during RT	Q3 months for 2 years post-RT
Evaluations						
History/Physical	≤21 days				X	X
Zubrod, weight	≤21 days				X	X
Histologic or cytologic tumor evaluation****	No Time Limit					
Protocol-specific AE evaluation	≤21 days				X	X

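### Section 9.3 applies limits from locally advanced disease to one pooled CFRT and SABR group, so on observed rates the pneumonitis limit can be met overall while CFRT exceeds it

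*Combined protocol and SAP*

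**What the plan says.** Section 9.3 compares adverse event rates for the treatment as a whole with three fixed limits: 13% for grade 3 or higher pneumonitis, 21% for grade 3 or higher esophagitis, and 20% for other grade 3 or higher events and drop-out. It describes these limits as "determined based on the published toxicity data for locally advanced lung cancer patients". It plans exact 95% confidence intervals but does not say whether the observed rate or a confidence limit must lie below the limit. Under the secondary endpoints, toxicity is to be summarised "overall and separately by grade and organ system"; modality is not listed.

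The enrolled population is wider than the source of the limits. Section 3.1 admits patients "to be treated with either conventionally-fractionated radiotherapy (CFRT) or hypo-fractionated stereotactic ablative radiotherapy (SABR", and adds: "Concurrent chemotherapy is allowed, but not required". For SABR, Section 3.2 states that "both early stage primary lung cancer patients and those with limited metastatic disease to the lungs are eligible". Section 11.1 says of brain MRI that "this is only required for locally advanced patients and for other patients, it is optional", so patients without locally advanced disease are expected. Section 9.2 accrues a single group of 34 with no quota by modality, and its accrual stop (more than five patients) is also pooled.

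The eligibility checklist in Appendix II does not fit this. Item 13, "Does the patient have locally advanced disease", is keyed Y, and item 16, "Does the patient have radiographic evidence of distant metastases", is keyed N.

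**The concern.** A pooled rate is an average over modalities, weighted by a mix that the plan leaves open. If SABR patients have less pneumonitis than CFRT patients, they pull the pooled rate down, and it can lie under 13% while the rate in CFRT does not. CFRT is the modality closest to the population behind the limits. A statement that the treatment is safe would then be read as covering CFRT without showing it.

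The documents make a lower SABR pneumonitis rate plausible. Section 1.4 assumes that risk rises with mean dose to high-functional lung, and Section 5.4.2 sets functional mean lung dose constraints of <19 Gy for CFRT and <4 Gy for SABR. They do not establish it. Fractionation differs (Section 5.1), the functional constraints are only guidelines for SABR with more than one target, and no SABR event rate is given.

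**Working it through.** **1. The plan's own figures.** Section 9.4 gives probabilities of at least one event of 94%, 99% and 99%, and standard errors of 8%, 9% and 9%, at true rates of 13%, 21% and 20%. Using 1 − (1 − p)^n and √(p(1 − p)/n):
- n = 20: 93.8%, 99.1%, 98.8%; SE 7.5%, 9.1%, 8.9%. These match.
- n = 34: 99.1%, 99.97%, 99.95%; SE 5.8%, 7.0%, 6.9%.

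The stated figures therefore describe about 20 evaluable patients, so step 2 uses both denominators. Section 9.4 uses one rate per endpoint for all patients.

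**2. Observed-rate reading, no assumed event rates.** The pooled group passes 13% with at most 4 of 34 (11.8%; 5/34 = 14.7% fails) or 2 of 20 (10.0%; 3/20 = 15.0% fails). Put all the events in CFRT:
- 34 patients, 4 events: 4/31 = 12.9% but 4/30 = 13.3%. The CFRT rate exceeds 13% once 4 or more of the 34 are SABR.
- 17 + 17: CFRT 4/17 = 23.5%, exact 95% CI 6.8% to 49.9%; pooled 4/34 = 11.8%, CI 3.3% to 27.5%.
- 20 evaluable, 2 events: 2/16 = 12.5% but 2/15 = 13.3%. The CFRT rate exceeds 13% once 5 or more are SABR.

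With no other grade 3 or higher event or drop-out, the 17 + 17 case meets all three limits (11.8%, 0%, 0%), and four patients do not reach the accrual stop.

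**3. Upper-limit reading.** With zero events the exact 95% upper limit is 1 − 0.025^(1/n). For 0/34 it is 10.3%; for 1/34 the exact upper limit is 15.3%. Only 0/34 passes, so an observed CFRT rate above 13% could not be declared safe.

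**4. How often, on stated assumptions.** Assume 17 + 17, a true CFRT pneumonitis rate of 20%, and a range of SABR rates; none of these is in the documents. Let C ~ Bin(17, 0.20) and S ~ Bin(17, p), independent. Pooled passes if C + S ≤ 4; CFRT alone passes if C ≤ 2 (2/17 = 11.8%), which has probability 31% in every row.

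| Assumed SABR rate | Pooled passes | CFRT fails, pooled passes | CFRT passes, pooled fails |
|---|---|---|---|
| 2% | 69% | 38% | 0.1% |
| 5% | 58% | 28% | 1% |
| 10% | 41% | 15% | 5% |
| 13% | 32% | 10% | 9% |
| 20% | 16% | 3% | 18% |

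**5. What a CFRT-only rule would do.** On the observed-rate reading, at a true 20%:
- n = 7, no event allowed: 0.8^7 = 21% pass.
- n = 8, one allowed: 0.8^8 + 8 × 0.2 × 0.8^7 = 50%.
- n = 15, one allowed: 17%.
- n = 17, two allowed: 31%.

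On the upper-limit reading, 0/26 has upper limit 13.2% and 0/27 has 12.8%, so fewer than 27 CFRT patients could never pass. The SE at 13% is √(0.13 × 0.87/34) = 5.8% with 34 patients and √(0.13 × 0.87/17) = 8.2% with 17.

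**The case against.** The strongest objection is that the problem exists only on one reading of the rule. That stands: on the upper-limit reading the masking in step 2 is impossible. But Section 9.3 does not adopt that reading, so the ambiguity itself needs settling.

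Second, the 17 + 17 example is possible but unlikely at the plan's own benchmarks. At rates of 21% and 20%, and assuming independence, 17 CFRT patients would all be free of esophagitis, other events and drop-out with probability (0.79 × 0.80)^17 = 0.04%. The pooled stop might also intervene. If CFRT rates were 20%, 21% and 20% and SABR rates 2% each, independent, the chance that a patient has any event would be 1 − 0.80 × 0.79 × 0.80 = 49% in CFRT and 1 − 0.98³ = 6% in SABR. More than five affected patients would then occur in 96% of trials, if every event fell during accrual. This stands as a limit on frequency. The stop ends accrual, however, and does not change how Section 9.3 judges the data.

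Third, the breakdown sentence sits under the secondary endpoints and does not forbid a table by modality, and Section 9.3 also correlates pulmonary toxicity with functional dose. Both points are true, but neither enters the safety decision.

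Fourth, Appendix II items 13 and 16, read literally, would remove the SABR patients at issue. Item 1 admits lung metastases for SBRT, item 14 is conditional on a yes to item 13, and Sections 3.2 and 11.1 expect such patients. This is better read as an inconsistency than as a restriction.

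A reader might also infer that the modality mix can flip the pooled verdict for a given set of events. At a fixed 34 it cannot: four CFRT events and no SABR events give 11.8% at every mix. Only the CFRT rate behind that count changes.

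**Conclusion.** The concern holds, conditionally. The limits are attributed to locally advanced disease, the judged group may include other patients in an open proportion, and no breakdown by modality is planned. On the observed-rate reading, a pooled pneumonitis rate under 13% does not show that CFRT met the limit; the two can part once 4 of 34 patients are SABR.

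The frequency is not known. The 38% in the first row of the table needs an even mix, a CFRT rate of 20% and a SABR rate of 2%. At a SABR rate of 13% the masking and its reverse nearly cancel, and at 20% the reverse dominates. The figures cover pneumonitis only; none is given for the joint three-endpoint decision.

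Two further inferences are not supported. A reader might conclude that pooling favours a safe verdict on all three endpoints, but the documents give no direction for esophagitis or other events. A reader might also take 4/17 as evidence that CFRT is unsafe, but its interval includes 13%. Confidence is moderate.

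**What to change.** In Section 9.3:
1. Report each primary endpoint for CFRT, for SABR and pooled, with exact 95% confidence intervals.
2. State whether the comparison with the limits uses the point estimate or a confidence limit.
3. Compare the 13%, 21% and 20% limits with the CFRT rates, noting that CFRT is the closer but not an identical population (chemotherapy is optional, and small-cell disease is eligible under Appendix II item 1). State that a pooled rate below the limits does not by itself support a safe conclusion for CFRT.
4. Give SABR a limit and source documented before analysis, or report it as an estimate with no safety statement.

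Separately, reconcile Appendix II items 13 and 16 with Sections 3.2 and 11.1.

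The cost is wording and one table; modality is already recorded in Appendix II item 2, and no extra enrolment is proposed. The price is the precision loss in step 5. A split removes dilution by SABR patients but, contrary to what a reader might expect, not dependence on the mix: the number of CFRT patients still drives a CFRT-only rule, and the pass probabilities in step 5 jump with n. With few CFRT patients, present the result as an estimate with its interval.
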